## **5.5 PHARMACOKINETIC , PHARMACODYNAMIC, AND PHARMACOGENOMIC/PHARMACOGENETIC ANALYSES**

Population pharmacokinetic (PK) and pharmacokinetic/pharmacodynamic (PK/PD) analysis are specified in the protocol but will not be discussed in this SAP. Separate analysis plan(s) for these analyses will be developed and finalized before the database lock.

### **5.5.1 Pharmacokinetic Analyses**

Not Applicable.

### **5.5.2 Pharmacodynamic Analyses**

Not Applicable.

### **5.5.3 Pharmacogenomic/Pharmacogenetic Analyses**

Not Applicable.

## **5.6 SAFETY ANALYSES**

All safety analyses will be performed on the Safety Analysis Set. Unless specified, all safety assessments will be summarized both overall (regardless of baseline platelet count) and within each baseline platelet count cohort. Safety data, presented by treatment group, will be summarized on an “as treated” basis using descriptive statistics or frequency count.

Study Day 1 for all safety analyses is defined as the date of the first dose of study drug. Unless specified otherwise, the baseline value will be defined as the most recent value reported prior to the first dose of study drug.

### **5.6.1 Extent of Exposure**

The extent of exposure to study drug will be characterized by duration of exposure (in days) for each treatment group.

Duration of exposure will be defined as the number of days between the date the subject received the first dose of study drug and the date the subject received the last dose of study drug, inclusive. Duration of exposure will be summarized using descriptive statistics by treatment group. In addition, the duration of exposure will be categorized, and will be summarized using frequency count by treatment group.

### **5.6.2 Adverse Events**

The AE verbatim descriptions (investigator terms from the CRF) will be classified into standardized medical terminology using the Medical Dictionary for Regulatory Activities (MedDRA). Adverse events will be coded to the MedDRA (Version 15.1 or higher) lower level term (LLT) closest to the verbatim term. The linked MedDRA preferred term (PT) and primary system organ class (SOC) will also be captured in the database.

A treatment-emergent AE (TEAE) is defined as an AE that

- Emerged during treatment (up to 30 days after the last dose of study drug), having been absent at pretreatment (Baseline) or
- Reemerged during treatment (up to 30 days after the last dose of study drug), having been present at pretreatment (Baseline) but stopped before the last dose of study drug plus 30 days, or
- Worsened in severity during treatment (up to 30 days after the last dose of study drug) relative to the pretreatment state, when the AE was continuous.

Only those AEs that are treatment emergent will be included in summary tables. All AEs, treatment emergent or otherwise, will be presented in subject data listings.

An overview table of TEAE, including number of subjects with TEAEs, treatment-emergent serious adverse events (SAEs), deaths, severe TEAEs, study drug related TEAEs, TEAEs leading to study drug withdrawal will be provided. In addition, the following summaries will be produced:

- Incidence of TEAEs by SOC and PT
- Incidence of treatment-related TEAEs by SOC and PT
- Incidence of procedure-related TEAEs by SOC and PT
- Incidence of TEAEs after procedure (with an onset date on or after Procedure Day) by SOC and PT
- Incidence of TEAEs related to platelet transfusion complications by SOC and PT
- Incidence of TEAEs by SOC, PT, and common terminology criteria for adverse events (CTCAE) grade
- Incidence of treatment-related TEAEs by SOC, PT, and CTCAE grade
- Incidence of TEAEs by SOC, PT, and relationship to treatment

If a subject experiences more than one TEAE within a preferred term, the subject will be counted only once in the calculation of incidence of TEAE within that preferred term. Similarly, if a subject experiences more than one TEAE within a SOC, the subject will be counted only once in the calculation of incidence of TEAE within that SOC. If a subject experiences more than one TEAE within a preferred term (or SOC), the occurrence with the highest CTCAE grade will be used in the calculation of the incidence of TEAE within that preferred term (SOC) by CTCAE grade. If a subject experiences more than one TEAE within a preferred term (or SOC), the occurrence considered most closely related to study drug will be used in the calculation of the incidence of TEAE with that preferred term (SOC) by relationship (given by investigator).

The following summaries will also be presented for the treatment-emergent SAEs:

- Incidence of treatment-emergent SAEs by SOC and PT
- Incidence of treatment-related treatment-emergent SAEs by SOC and PT

- Incidence of treatment-emergent SAEs by SOC, PT, and relationship to treatment.

In addition, number (percentage) of subjects with TEAEs and treatment-related TEAEs leading to discontinuation from study treatment will also be summarized by MedDRA SOC, PT for each treatment group.

### 5.6.3 Laboratory Values

Laboratory results will be summarized using Système International (SI) units, as appropriate. With the exception of urinalysis, platelet function tests and platelet count (which is considered as an efficacy parameter), for all quantitative parameters listed in [protocol Section 9.5.1.5 Safety Assessments \(Laboratory Measurements\)](#), the actual value and the change from baseline will be summarized by visit and treatment group using descriptive statistics. Analysis of changes from baseline will be based on the number of subjects with both nonmissing baseline and relevant postbaseline results.

Laboratory test results will be assigned a low/normal/high (LNH) classification according to whether the value is below (L), within (N), or above (H) the laboratory parameter's reference range. Shifts from baseline (LNH) to Procedure Day and to the end of the Follow-up Phase will be presented for each laboratory parameter. Similar shift tables from baseline (LNH) to the highest/lowest postbaseline LNH classification will also be provided. A subject will be counted once in highest LNH classification and once in the lowest LNH classification.

The Sponsor's Grading for Laboratory Values (see [Appendix 1](#)) presents the criteria that will be used to identify subjects with treatment-emergent markedly abnormal laboratory values (TEMAV). Except for phosphate, a TEMAV is defined as a postbaseline value with an increase from baseline to a grade of 2 or higher. For phosphate, a TEMAV was defined as a postbaseline value with an increase from baseline to a grade of 3 or higher. When displaying the incidence of TEMAVs, each subject will be counted once in the laboratory parameter high and in the laboratory parameter low categories, as applicable.

### 5.6.4 Vital Signs

For each vital signs parameters (diastolic and systolic blood pressure, pulse, respiration rate, temperature and weight), the actual value and changes from baseline will be summarized by visit and treatment group using descriptive statistics. Analysis of changes from baseline will be based on the number of subjects with both nonmissing baseline and relevant postbaseline results.

### 5.6.5 Electrocardiograms

For each electrocardiogram (ECG) parameter (including PR interval, RR interval, QRS interval, QT interval, QTcB interval, QTcF interval and heart rate), the actual value and change from baseline will be summarized by visit and treatment group using descriptive statistics. ECG interpretation (categorized as normal and abnormal) will be summarized using frequency count at each visit by treatment group.

Maximum postbaseline QTcB and QTcF will also be tabulated by treatment group as follows:

- Number and percentage of subjects in the borderline (430-450 msec), abnormal category (> 450 msec), and highly abnormal (>500 msec) during the treatment, and
- Number and percentage of subjects with an increment of 30-60 msec and > 60 msec from the baseline visit.

QT will be corrected primarily using Fridericia's formula (QTcF) and also using Bazett's formula (QTcB) defined as:

- QTcF is the heart rate corrected QT interval by Fridericia's formula:  $QTcF = QT/(RR)^{0.33}$
- QTcB is the heart rate corrected QT interval by Bazett's formula:  $QTcB = QT/(RR)^{0.5}$ .

### 5.6.6 Other Safety Analyses

#### 5.6.6.1 Adverse Events of Special Interest

The incidence of treatment-emergent adverse events and treatment-related, treatment-emergent adverse events of special interest will be summarized by treatment group.

Adverse events of special interest include:

- Recurrence of thrombocytopenia (platelet count of  $<10 \times 10^9/L$  and  $10 \times 10^9/L$  less than baseline count within 30 days of discontinuation)
- Thromboembolic events
- Bleeding events (WHO Grade 2 to 4)

Recurrence of thrombocytopenia events include the adverse events with MedDRA preferred term belonging to 2nd level Standardized MedDRA Query (SMQ) 'Haematopoietic thrombocytopenia' and with 'Event of Special Interest per Protocol Definition' checked as 'Yes' on the AE CRF page.

Thromboembolic events include the adverse events with MedDRA preferred term belonging to SMQ 'Embolic and thrombotic events'.

Bleeding events (WHO Grade 2 to 4) include the adverse events with MedDRA preferred term belonging to 2nd level SMQ 'Haemorrhage terms (excl laboratory terms)' and with WHO Bleeding Scale score 2 to 4.

Additionally the incidence of treatment-emergent adverse events and treatment-related, treatment-emergent adverse events for thromboembolic events will be summarized by treatment group and by HCC status.

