Liver function tests	alanine aminotransferase, alkaline phosphatase, aspartate aminotransferase, direct bilirubin, total bilirubin, gamma-glutamyl transpeptidase
Renal function parameters	blood urea nitrogen, creatinine
Other	albumin, calcium, cholesterol, creatine phosphokinase with fractionation, globulin, glucose, lactate dehydrogenase, phosphorus, total protein, triglycerides, uric acid
Urinalysis	bacteria, casts, crystals, epithelial cells, glucose, ketones, occult blood, pH, protein, RBCs, specific gravity, WBCs
Protocol specified	
Females only	serum beta-human chorionic gonadotropin pregnancy tests, urine pregnancy tests
Platelet function tests ^a	eg, p-selectin and integrin IIbβ3 with and without an agonist. The following agonists will be used: 0.5 μM ADP, 20 μM ADP, 1.5 μM TRAP, or 20 μM TRAP (eg, platelet aggregation with an agonist. ADP will be used as the agonist) (revised per Amendment 02)

ADP = adenosine diphosphate, RBC = red blood cell, TRAP = thrombin receptor agonist peptide, WBC = white blood cell

a: Performed only at selected sites

Clinical laboratory tests during the study will be performed by the designated central laboratory. All blood and urine samples will be collected and sent to the central laboratory on the day of collection unless otherwise instructed. When a hematology test is required, 2 blood samples will be collected: 1 for central laboratory analysis and 1 for local laboratory analysis. Investigators will utilize the platelet count result received from the local laboratory hematology test analysis to qualify subject's entry into the study, and also for clinical assessments.

Only platelet count data from local laboratories, including the date and clock time of collection of the sample, will be collected and entered into the CRF for analysis. All other hematological parameters will be collected and loaded into the database for analysis according to results derived from the designated central laboratory.

A laboratory abnormality may meet the criteria to qualify as an AE as described in this protocol (see Adverse Events and Other Events of Interest) and the CRF Completion Guidelines. In these instances, the AE corresponding to the laboratory abnormality will be recorded on the Adverse Event CRF.

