- Is outside normal limits at baseline and increases in severity to the sponsor's grading criteria for laboratory values of Grade 4 or above. These abnormalities are automatically considered to be serious, with the exception of expected and reproducible hematologic abnormalities.
- Is otherwise considered by the investigator to meet serious criteria as defined in [Section 9.5.1.5](#) (Serious Adverse Events and Other Events of Interest)

Significant laboratory abnormalities should not be listed as separate AEs or SAEs if they are considered to be part of the clinical syndrome that is being reported as an AE or SAE.

REPORTING OF STUDY-SPECIFIC EVENTS

Study-specific events (ie, recurrence of thrombocytopenia [defined as a platelet count of $<10 \times 10^9/L$ and $10 \times 10^9/L$ less than baseline count within 30 days of discontinuation]); thromboembolic events; bleeding events (WHO Grade 2 to 4); and platelet transfusion-related complications should be entered on the Adverse Event CRF and reported using the procedures detailed in Reporting of Serious Adverse Events ([Section 9.5.4.1](#)), even if the study-specific event does not meet serious criteria. If the event does not meet serious criteria, it must still be reported using the SAE form and in an expedited manner but should be noted as nonserious on the SAE form and the Adverse Event CRF. All liver transplantations will be captured as SAEs.

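### Recurrence of thrombocytopenia is defined by platelet counts but tabulated only from flagged adverse events, with no check against the recorded counts

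*SAP*

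**What the plan says.** Platelet counts below are in units of 10⁹/L.

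- **Definition.** SAP 5.6.6.1 lists recurrence of thrombocytopenia as one of three adverse events of special interest: a count below 10 that is also 10 "less than baseline count within 30 days of discontinuation". Protocol 9.5.4.3 carries the same numeric rule ("recurrence of thrombocytopenia [defined as a platelet count of" and so on).
- **How cases are identified.** The same SAP section says: "Recurrence of thrombocytopenia events include the adverse events with MedDRA preferred term belonging to" the SMQ 'Haematopoietic thrombocytopenia' "and with 'Event of Special Interest per Protocol Definition' checked as 'Yes' on the AE CRF page". Both conditions must hold. No step refers to the counts.
- **The other two categories.** Thromboembolic events need only an SMQ term. Bleeding events need an SMQ term and a WHO score of 2 to 4. Only recurrence depends on a tick-box.
- **What sites must do.** Protocol 9.5.4.3 says that such events "should be entered on the Adverse Event CRF and reported using the procedures detailed in Reporting of Serious Adverse Events", even when not serious.
- **What data exist.** Protocol 9.5.1.5 provides that "Only platelet count data from local laboratories", with date and time, "will be collected and entered into the CRF for analysis".
- **Laboratory tables.** SAP 5.6.3 opens its value and change-from-baseline summaries "With the exception of urinalysis, platelet function tests and platelet count (which is considered as an efficacy parameter"). The grading table in SAP 13.1 nevertheless has a platelet row.

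**The concern.** Of the three categories, this is the only one defined wholly by a laboratory measurement, and the measurement is in the database. The SAP's route instead needs three site or coding steps to go right: the low count is reported as an AE, the term codes into the SMQ, and the box is ticked. If any fails, a subject who meets the definition is missing from the table. Conversely, no numeric check is applied, so an AE in the SMQ with the box ticked in error is counted even if its count does not meet the definition.

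What is at stake is the accuracy of a small-number safety table in a drug class where the fall in counts after stopping is an event of declared interest. With few events, one or two misclassified subjects can change how the arms compare.

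**Working it through.** The plan gives neither an incidence for this event nor a completeness for the tick-box, so there is no figure to reproduce. The checks below are of logic and of scale.

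**1. Definition against counting rule**

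| Recorded counts meet the definition | AE in the SMQ with box 'Yes' | In the special-interest table | Correct |
|---|---|---|---|
| Yes | Yes | Yes | Yes |
| Yes | No | No | No: omitted |
| No | Yes | Yes | No: wrongly included |
| No | No | No | Yes |

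Both off-diagonal rows are open.

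**2. Does the markedly-abnormal (TEMAV) table act as a backstop?** SAP 5.6.3 counts a rise from baseline to Grade 2 or higher. SAP 13.1 puts platelets from 25 to below 50 in Grade 3 and below 25 in Grade 4. Take integer baselines 10 to 50, later counts 0 to 9, and a fall of at least 10 (my reading of the definition):
- Baselines 10 to 19 give 1 + 2 + … + 10 = 55 qualifying pairs; baselines 20 to 24 give 5 × 10 = 50. All 105 start in Grade 4, cannot rise in grade, and are missed.
- Baselines 25 to 50 give 26 × 10 = 260 pairs. All become Grade 4 and are caught, but in the same cell as falls to between 10 and below 25, which do not qualify.
- So 105 of 365 pairs are missed. These are grid cells, not a patient rate.

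**3. Other outputs**
- Low/normal/high shifts (SAP 5.6.3): Grade 1 for platelets runs from the lower limit of normal down to 75, so that limit lies above 75. A subject with a baseline below 50 starts 'low', and a further fall produces no shift.
- By-visit platelet counts (SAP 5.4.3.1): summary statistics include a minimum (SAP Section 5), so a very low value may be visible. SAP 8.1 takes one visit per window, and the summary does not count subjects meeting the rule.
- Responder thresholds (SAP 5.4.3.2) are 50, 75 and 200, all upward.

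**4. Reporting triggers.** The laboratory-AE trigger in Protocol 9.5.1.5 is a rise of at least 2 grades. From a baseline below 50 (Grade 3 or 4), a fall below 10 is a rise of at most one grade. The significant-abnormality rule in Protocol 9.5.4.3 needs worsening to Grade 4, so it covers falls from 25 or more but not from below 25. For the latter, reporting rests on the site recognising the study-specific definition.

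**5. Weight of one subject** (planned sizes, SAP Section 4)
- Overall: 1/133 = 0.75% on avatrombopag; 1/67 = 1.5% on placebo.
- Within a cohort: 1/67 = 1.5%; 1/33 = 3.0%.
- Exact upper 95% limit on avatrombopag: with 0 of 133, 1 − 0.025^(1/133) = 2.7%; with 1 of 133, the 97.5th percentile of Beta(2, 132) = 4.1%.

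**6. Illustration only.** If each true event is flagged independently with probability s (assumed), the chance of losing at least one of three is 1 − s³: 14% at s = 0.95, 27% at 0.90, 49% at 0.80.

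**7. Points a derivation must settle**
- Baseline: SAP Figure 1 uses the mean of the Screening and Baseline counts; SAP 5.6 uses the last pre-dose value unless otherwise specified. From a baseline of 20 or more, any count below 10 is a fall of more than 10, so the choice matters only when one of the two values is below 20.
- Window: the last dose is on Day 5, and 5 + 30 = Day 35. Visit 6 is Day 35 (+3 days), so counts on Days 36 to 38 fall outside 30 days.
- Visit 3 is Day 4 (±1), normally before the last dose, so it contributes little.

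**The case against.** The best reply has four parts.

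**Safeguards exist.** Sites must enter the event as an AE and report it through the SAE procedure (Protocol 9.5.1.5 and 9.5.4.3). Worsening to Grade 4 has its own reporting duty, and TEMAV and the by-visit summaries show low counts. This stands in part. A reader might take the platelet exception in SAP 5.6.3 to mean that nothing else would reveal an unflagged count. The text does not support that: the exception covers the value and change summaries only, and platelets remain in the grading table. The backstops are still incomplete, as steps 2 to 4 show, and none is an analysis rule for this event.

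**Errors run both ways.** A reader might infer that the rule can only lose events and that the rate will be understated. The documents do not establish either. A mistaken tick adds a case, and nothing shows which error is commoner. Nor do they show that sites would avoid recording a further fall in subjects who start low; the stated duties point the other way.

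**AE-based counting is partly deliberate.** The section also tabulates treatment-related events, and a laboratory-derived event carries no causality assessment. This stands, and is why the AE table should be kept. Raw counts can also be spurious: Protocol 9.1.1.1 mentions clumped platelets as a reason for repeat testing.

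**Details may be elsewhere.** Programming specifications and table shells are separate documents (SAP Sections 9 and 11), so a reconciliation there cannot be excluded. It would still need stating in the SAP.

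**Conclusion.** The point holds as a modest refinement. SAP 5.6.6.1 states a count-based definition and then applies an AE-and-tick-box rule with no cross-check, so the special-interest table may omit true cases and include false ones. What is affected is that table, not the database: the counts remain available.

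How often this would happen cannot be computed, because the documents give neither an incidence nor a flagging completeness. The 0.75% and 1.5% figures show only the weight of one subject at the planned arm sizes, and the 14% to 49% range rests wholly on assumed completeness. The conclusion also assumes that the unseen programming documents do not already reconcile the two sources. It does not bear on the efficacy analyses.

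**What to change.** Keep the AE-based table in SAP 5.6.6.1, since it alone carries causality, and add:

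1. A count-derived incidence of recurrence by treatment group, overall and within each cohort, applying the protocol's own definition to every recorded local platelet count after the last dose, including unscheduled ones.
2. A listing of subjects who meet one source but not the other, reviewed before unblinding, with any count judged spurious documented.
3. A statement of which baseline applies (the mean of two counts or the last pre-dose value), whether the required fall means at least 10 × 10⁹/L, and how counts on Days 36 to 38 are treated against the 30-day window.

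The cost is a small amount of programming from data already collected, plus the time to review discordant and possibly spurious counts. No new data collection is needed.

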9.5.1.3 Efficacy Assessments

The timing of assessments is described in the Schedule of Assessments/Procedures ([Table 5](#)).

NUMBER OF PLATELET TRANSFUSIONS

The incidence of platelet transfusions will be monitored by the investigator (or appropriately delegated study site personnel) from randomization. The number of transfusions administered (if used), along with date and start/stop times, will be specified and recorded in the CRF. In order to minimize missing data for the primary endpoint, “Not Done” (or “Not Applicable”) will be collected on the CRF to indicate subjects who did not receive a platelet transfusion.

ANY RESCUE PROCEDURE FOR BLEEDING

Any rescue procedure for bleeding will be monitored by the investigator (or appropriately delegated study site personnel) from randomization onwards. Any rescue procedure for bleeding, including number of transfusions administered (if used), along with start and end dates/times, will be recorded. In order to minimize missing data for the primary endpoint, “Not Done” (or “Not Applicable”) will be collected on the CRF to indicate subjects who did not receive rescue therapy.

The following are considered as rescue procedures when used specifically for bleeding:

- Platelet transfusion
- FFP
- Cryoprecipitate
- Vitamin K (phytonadione)
- Desmopressin
- Recombinant activated factor VII
- Aminocaproic acid
- Tranexamic acid (added per Amendment 01)
- Whole blood transfusion
- Packed red cell transfusion
- Surgical intervention or interventional radiology

PLATELET COUNTS

Platelet count by local laboratory will be measured in all subjects at Screening (Days -14 to -1) and at Baseline (Day 1), then on the Procedure Day (Day 10), 7 days postprocedure and Day 35. Screening and Baseline platelet counts must be measured at least 1 day apart with neither platelet count $>60 \times 10^9/L$ for eligibility. The mean of these 2 platelet counts (mean baseline platelet count $<50 \times 10^9/L$) will be used for entry criteria.

BLEEDING EVENTS

All bleeding events will be assessed by the investigator (or appropriately delegated study site personnel) from randomization utilizing the WHO bleeding score ([Table 2](#)) and the Bleeding Academic Research Consortium (BARC) bleeding scale ([Table 3](#)).

Table 2 WHO Bleeding Score Categories

Bleeding Grade	Description
Grade 0	No bleeding
Grade 1	Petechial bleeding
Grade 2	Mild blood loss (clinically significant)
Grade 3	Gross blood loss, requires transfusion (severe)

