- Incidence of TEAEs by SOC, PT, and CTCAE Grade
- Incidence of TEAEs by SOC, PT, and relationship to treatment.

A subject will be counted only once within a SOC and PT, even if the subject experienced more than 1 TEAE within a specific SOC and PT.

The following summaries will also be presented for the treatment-emergent SAEs:

- Incidence of treatment-emergent SAEs by SOC and PT
- Incidence of treatment-related treatment-emergent SAEs by SOC and PT
- Incidence of treatment-emergent SAEs by SOC, PT, and relationship to treatment

In addition, subjects with TEAEs, treatment-related TEAEs leading to discontinuation from study treatment, and AEs of special interest for this study (including recurrence of thrombocytopenia, thromboembolic events and bleeding events [WHO Grade 2 to 4]) will also be summarized for each treatment group.

LABORATORY VALUES

Laboratory results will be summarized using Système International units, as appropriate. With the exception of urinalysis, platelet function tests, and platelet count (which is considered as an efficacy parameter), for all quantitative parameters listed in [Section 9.5.1.5 Safety Assessments \(Laboratory Measurements\)](#), the actual value and the change from baseline to Procedure Day and to the end of the Follow-up Phase will be summarized by treatment group using descriptive statistics. Analysis of changes from baseline will be based on the number of subjects with both nonmissing baseline and relevant postbaseline results.

Laboratory test results will be assigned a low/normal/high (LNH) classification according to whether the value was below (L), within (N), or above (H) the laboratory parameter's reference range. Shifts from baseline (LNH) to Procedure Day and to the end of the Follow-up Phase will be presented for each laboratory parameter. Similar shift tables from baseline (LNH) to the highest/lowest postbaseline LNH classification will also be provided.

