#### 5.4.3.5 Proportion of subjects with a WHO bleeding score $\geq 2$ after randomization and up to 7 days following an elective procedure

Proportion of subjects with a WHO bleeding score  $\geq 2$  after randomization and up to 7 days following an elective procedure, will be summarized by treatment group within each baseline cohort, and by overall treatment groups, regardless of the baseline platelet count cohorts.

A 2-sided 95% CI will be constructed by baseline cohort, and for the overall treatment difference (avatrombopag minus placebo) using normal approximation method for the proportion of subjects with the qualified WHO bleeding score.

Subjects with missing WHO bleeding score will be considered as having a WHO bleeding score  $\geq 2$  in this analysis.

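### SAP 5.6.6.1 adds a MedDRA term filter to the protocol's definition of bleeding of special interest, so the AESI table can omit bleeds that the investigator scored WHO Grade 2 to 4

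*SAP*

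**What the plan says.** The protocol names this event in three places, each time by grade and with no coding condition: in 9.5.1.5 among the other events of interest, in 9.5.4.3 and in 9.7.1.8. For reporting, 9.5.4.3 has "thromboembolic events; bleeding events (WHO Grade 2 to 4); and platelet transfusion-related complications should be entered on the Adverse Event CRF". For analysis, 9.7.1.8 speaks of "AEs of special interest for this study (including recurrence of thrombocytopenia, thromboembolic events and bleeding events [WHO Grade 2 to 4" and has these events summarised by treatment group. Grading is meant to be complete. Protocol 9.5.1.3 states: "All bleeding events will be assessed by the investigator (or appropriately delegated study site personnel) from randomization utilizing the WHO bleeding score".

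SAP 5.6.6.1 repeats the same label in its list of AESIs and then gives the derivation. The preferred term must belong to the second-level "SMQ 'Haemorrhage terms (excl laboratory terms)' and with WHO Bleeding Scale score 2 to 4". For comparison, the thromboembolic AESI rests on coding only: "Thromboembolic events include the adverse events with MedDRA preferred term belonging to SMQ 'Embolic and thrombotic events". Recurrent thrombocytopenia uses an SMQ plus a CRF flag.

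SAP section 7, which records changes in the planned analyses, does not mention the added bleeding condition, and no rationale for it appears elsewhere.

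**The concern.** A WHO score of 2 to 4 on an adverse event is the investigator's judgement that the event was a bleed of at least clinically significant degree (WHO Grade 2 in Protocol Table 2). A later filter on the coded term cannot add any event to that set. It can only remove some. What it removes are events that meet the protocol definition but whose verbatim wording led to a code outside the SMQ.

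The table in question is a main safety display for a drug meant to reduce the need for transfusion around a procedure. The Amendment 04 rationale says that bleeding events were rarer than expected. With few events, one omission is visible in the arm's rate, and the table may disagree with the unfiltered bleeding summaries for a reason that the SAP does not state.

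**Working it through.** The plan states no figure on this point, so there is nothing to reproduce. The check sets the definitions side by side.

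**Step 1. Compare the two sets.** Let G be the adverse events with a WHO score of 2 to 4, and S those with a preferred term in the non-laboratory haemorrhage SMQ.

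- Protocol definition: G.
- SAP derivation: G and S.
- Difference: G and not S.

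| Adverse event record | Protocol | SAP 5.6.6.1 |
|---|---|---|
| WHO 2 to 4, term inside SMQ | counted | counted |
| WHO 2 to 4, term outside SMQ | counted | **omitted** |
| WHO 0 or 1, term inside SMQ | not counted | not counted |
| No WHO score, term inside SMQ | not counted | not counted |

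Only the second row differs, and it differs in one direction.

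**Step 2. Find where a second-row event would still appear.**

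| Output | Population | Term filter | Time limit | Treatment-emergent | By relatedness | Totals WHO 2 to 4 bleeding |
|---|---|---|---|---|---|---|
| SAP 5.4.3.4, highest WHO and BARC score | FAS | none | none stated | no | no | yes, by highest score |
| SAP 5.4.3.5, WHO score 2 or more | FAS | none | 7 days after procedure | no | no | yes |
| SAP 5.6.2, SOC/PT tables | Safety Set | none | 30 days after last dose | yes | yes | no (by term and CTCAE grade) |
| SAP 5.6.2, listings | all AEs | none | none | no | no | no (subject level) |
| SAP 5.6.6.1, AESI table | Safety Set | **SMQ** | 30 days after last dose | yes | yes | yes |

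The event stays in the report. But only the last row combines the Safety Set, treatment-emergence, relatedness and a total of graded bleeding, and that row carries the filter.

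**Step 3. Size per event.** The documents do not list the SMQ's contents, so the number of second-row events cannot be estimated, and zero is possible. What can be given is the effect of one omitted event that is its subject's only qualifying one. The denominators are the planned randomised numbers in SAP section 4 (133 and 67 overall; 67 and 33 per baseline cohort), because SAP 5.6 reports safety both overall and by cohort:

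- Overall: avatrombopag 1/133 = 0.75 percentage points; placebo 1/67 = 1.5.
- Within a cohort: avatrombopag 1/67 = 1.5 percentage points; placebo 1/33 = 3.0.

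Actual Safety Set denominators may differ slightly.

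**The case against.** The best defence is that the protocol speaks of bleeding events with a grade, not of a grade by itself. On this view the SMQ is only the SAP's way of recognising a bleeding event among coded terms. Protocol 9.7 and 9.7.1 leave analytical detail to the SAP, and recurrent thrombocytopenia has a similar two-part rule. The table is descriptive, with no hypothesis test, and SAP 5.4.3.4 gives an unfiltered count by arm.

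Part of this stands. It limits the consequence to one table. It does not justify the filter, because a record carrying a WHO score of 2 to 4 has already been recognised as a bleed by the investigator. An SMQ is needed for thromboembolic events, where the protocol supplies no grade; here it does.

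Several stronger readings are tempting, and the documents do not support them:

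- *Graded bleeds are lost, especially late ones.* SAP 5.4.3.4 has no term filter and no 7-day limit, and Protocol Table 5 schedules bleeding assessment through Visit 6. Late graded bleeds are therefore tabulated by arm, though on the FAS.
- *Haemorrhage events without a score are a protocol-SAP conflict.* They fail the protocol definition too, since it depends on the grade.
- *The SAP treats the same subject in opposite ways.* SAP 5.4.3.5 does say "Subjects with missing WHO bleeding score will be considered as having a WHO bleeding score" of 2 or more, but that is a subject-level rule for an exploratory endpoint. SAP 5.6.6.1 selects adverse events, and safety analyses use observed data. An unscored event does not by itself make the subject's WHO assessment missing.
- *BARC Types 3a and 3b show that bleeds will be coded as laboratory terms.* Protocol Table 3 requires overt bleeding as well as the haemoglobin fall. Protocol 9.5.1.5 also discourages listing a laboratory value separately when it belongs to a reported syndrome.
- *A probability of omission can be stated.* It would rest wholly on an assumed rate of coding outside the SMQ, which the documents do not give.

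**Conclusion.** The discrepancy is real and narrow. SAP 5.6.6.1 counts a subset of what the protocol defines as bleeding of special interest, and the difference consists only of events scored WHO 2 to 4 and coded outside one SMQ. The AESI table may therefore undercount, and it cannot overcount, relative to the protocol. It may also differ from SAP 5.4.3.4 and 5.4.3.5 for this reason, on top of the expected differences in population, window and missing-score handling.

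The size is unknown and may be zero. No efficacy conclusion or error rate is affected.

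The conclusion assumes that the SAP sentence is the working definition. Its verb could be read as non-exclusive, but no other derivation is given. It also assumes that the WHO score is available on the adverse event record, which the SAP rule itself presupposes. The point is worth correcting because the rule can only remove protocol-defined safety events from the one table designed to count them.

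**What to change.** In SAP 5.6.6.1, replace the bleeding derivation with text such as: *Bleeding events of special interest are all treatment-emergent adverse events with a WHO Bleeding Scale score of 2 to 4, whatever the preferred term. The haemorrhage SMQ is used only to raise data queries before database lock, where term and score disagree or where the score is missing.*

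Optionally, show haemorrhage-SMQ events that still have no score after querying on a separate line, outside the main count. Record the change and its reason in SAP section 7.

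The cost is one SAP sentence, one programming condition and some query work before lock. The downside is that the reported count may rise slightly. No test, endpoint or sample size changes.
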